#### 7.2.7.1 **Protocol-Specific Expedited Adverse Event Reporting Exclusions:**

Events **not** considered to be serious adverse events in this trial are:

- Lymphopenia (grades 2-4)
- A visit to the emergency room or other hospital department < 24 hours, that does not result in admission (unless considered an important medical or life-threatening event)
- Emergency outpatient treatment for an event not fulfilling the serious criteria outlined above and not resulting in inpatient admission
- Elective surgery, planned prior to signing consent
- Routine health assessment requiring admission for baseline/trending of health status (e.g., routine colonoscopy)
- Hospitalization for routine treatment or monitoring of the studied indication, not associated with any deterioration in condition, or for elective procedures
- Hospitalization for scheduled debulking surgery
- Hospitalization for seizure, if felt related to patient's underlying disease
- Hospitalization for elective or pre-planned treatment for a pre-existing condition that did not worsen

CONFIDENTIAL

This document is confidential. Do not disclose or use except as authorized.

- Hospitalization for respite care not associated with an adverse event attributed to the study drug
- Hospitalization for treatment of patient's underlying disease (e.g. admission after patient is removed from active study treatment for craniotomy)
- Medical/surgical admission other than to remedy ill health and planned prior to entry into the study. Appropriate documentation is required in these cases
- Admission encountered for another life circumstance that carries no bearing on health status and requires no medical/surgical intervention (eg, lack of housing, economic inadequacy, caregiver respite, family circumstances, administrative reason).

#### **7.2.8 Potential Drug Induced Liver Injury (DILI) Definition:**

Wherever possible, timely confirmation of initial liver-related laboratory abnormalities should occur prior to the reporting of a potential DILI event. All occurrences of potential DILIs, meeting the defined criteria, must be reported as SAEs.

Potential drug induced liver injury is defined as:

1. ALT or AST elevation > 3 times upper limit of normal (ULN)  
AND
2. Total bilirubin > 2 times ULN, without initial findings of cholestasis (elevated serum alkaline phosphatase)  
AND
3. No other immediately apparent possible causes of AST/ALT elevation and hyperbilirubinemia, including, but not limited to, viral hepatitis, pre-existing chronic or acute liver disease, or the administration of other drug(s) known to be hepatotoxic.

#### **7.3 Procedures for AE and SAE Recording and Reporting**

Participating investigators will assess the occurrence of AEs and SAEs at all participant evaluation time points during the study.

All AEs and SAEs whether reported by the participant, discovered during questioning, directly observed, or detected by physical examination, laboratory test or other means, will be recorded in the participant's medical record and on the appropriate study-specific case report forms (eCRFs).

#### **7.4 Expedited Adverse Event Reporting**

**7.4.1** Investigators **must** report to the Overall PI and BMS any serious adverse event (SAE) that occurs after a subject's consent, during treatment, or within 100 days of the last dose of treatment (or until the start of new anti-cancer treatment, whichever comes first) via the appropriate applicable reporting form (MedWatch 3500A and/or local institutional IRB submission form).

**7.4.2 DF/HCC Expedited Reporting Guidelines**

Investigative sites within DF/HCC will report AEs directly to the DFCI Office for

CONFIDENTIAL

This document is confidential. Do not disclose or use except as authorized.

Human Research Studies (OHRS) per the DFCI IRB reporting policy.

#### **7.4.3 Expedited Adverse Event Reporting Requirements (By Site to Overall PI and BMS)**

The study must be conducted in compliance with local safety reporting requirements, and reporting requirements of the principal investigator.

Each adverse event will be assessed to determine if it meets the criteria for reporting. Adverse event reporting is to occur according to the site's specific IRB guidelines, and as outlined in this Section. Any serious adverse event occurring after the participant has initiated study treatment and until 100 days after the participant has stopped the study drug or the start of new anti-cancer treatment (whichever comes first) must be reported. Serious adverse events must be followed until resolution.

Investigators **must** report to the Overall PI any serious adverse event (SAE) that occurs after the participant has signed consent to participate in the study, during treatment, and until 100 days after the last dose of treatment or the start of new anti-cancer treatment (whichever comes first) on the local institutional SAE form.

It is the responsibility of each participating investigator to report adverse events to the Overall PI, BMS, DF/HCC IRB, and/or others as described below. The Overall PI or representative Coordinating Center personnel will ensure the report is forwarded to the proper parties, as appropriate.

Adverse event reporting by each site is detailed in Table 7.4.3-1.

For trials where a DF/HCC investigator is serving as the Overall Principal Investigator, each participating institution **must** abide by the reporting requirements set by the DF/HCC. This applies to any medical event equivalent to an unexpected grade 2 or 3 with a possible, probable or definite attribution, any grade 4 unexpected toxicities, and grade 5 (death) regardless of attribution.

Whenever feasible, the participating investigator should provide follow-up information on the serious adverse event within the following 24-48 hours. Follow-up information should describe whether the event has resolved or continues, if and how the event was treated, and whether the participant will continue or discontinue study participation.

**Note:** If the participant is in long term follow up, report the death at the time of continuing review.

CONFIDENTIAL

This document is confidential. Do not disclose or use except as authorized.

Table 7.4.3-1: Reporting to Study's Overall PI, BMS, and IRB:

Adverse Event Characteristics				Notification Requirement		
Seriousness	Toxicity	Known correlation	Attribution to study drug(s)	Bristol-Myers Squibb Company (BMS)	[name]: Overall PI	DF/HCC IRB
Serious	Any	Any (Expected or Unexpected)	Any	Within 24 hours from notification d  Via Fax Use Facsimile Coversheet b and Medwatch 3500A c	Within 24 hours from notification d  Via Email a Use Facsimile Coversheet b and Medwatch 3500A c	As needed if required per local IRB
Any	Potential Drug Induced Liver Injury (DILI) e , Any Grade, Overdose, or Pregnancy	Any (Expected or Unexpected)	Any	Within 2 working days from notification d	Within 2 working days from notification d	To be submitted within IRB established reporting timelines.  Please ensure that [name] prospectively approves all submissions.

a. Email the Medwatch 3500A form, facsimile coversheet, and the IRB SAE report to the DFCI Coordinating Site with the subject title as "Nivolumab SAE" to [NeuroOnc\\[contact]](mailto:[contact]). All SAE reports received at this account are forwarded immediately to study's Overall PI, [name], and to the DFCI Coordinating Center personnel.  
b. Facsimile Coversheet is found in Appendix D. Adverse Event Reporting Facsimile Coversheet contains all FAX numbers/e-mails and destinations.  
c. Medwatch 3500A downloadable form at <http://www.fda.gov/medwatch/getforms.htm>  
d. In the event that the participating investigator does not become aware of the serious adverse event immediately (e.g., participant sought treatment elsewhere), the participating investigator is to report the event within 24 hours after learning of it and document the time of his or her first awareness of the adverse event.  
e. See section 7.2.8 of the protocol for definition of Potential Drug Induced Liver Injury (DILI)

CONFIDENTIAL

This document is confidential. Do not disclose or use except as authorized.

## 7.5 Reporting of Pregnancy

If, following initiation of the investigational product, it is subsequently discovered that a study subject is pregnant or may have been pregnant at the time of investigational product exposure (including at least 5 months after the last dose of Nivolumab and/or Ipilimumab for women), the investigational product will be permanently discontinued in an appropriate manner (e.g., dose tapering if necessary for subject safety).

The investigator must immediately notify Worldwide Safety @ BMS of this event via the Pregnancy Surveillance Form in accordance with SAE reporting procedures.

In addition, any pregnancy that occurs in a female partner of a male study participant should be reported to BMS. Information on this pregnancy will be collected on the Pregnancy Surveillance Form (also in accordance with SAE reporting procedures).

- This will include any pregnancy that occurs within 7 months post-treatment in male participants.
- In order for Sponsor or designee to collect any pregnancy surveillance information from the female partner, the partner must sign an informed consent form for disclosure of this information.

Follow-up information regarding the course of the pregnancy, including perinatal and neonatal outcome, and - where applicable - offspring information, must be reported on the Pregnancy Surveillance Form [provided upon request from BMS]. Details on the pregnancy will be collected for safety analysis throughout the pregnancy and for up to one year following the birth of the infant. The Pregnancy Surveillance Form provided by BMS will be completed and submitted to study sponsor and BMS Worldwide Safety at a frequency dependent upon the pregnancy; updates provided when new information is available. Initial pregnancy notifications as well as any complications identified will be submitted in accordance with SAE reporting procedures (within 24 hours of notification).

## 7.6 Overdose

An overdose is defined as the accidental or intentional administration of any dose of a product that is considered both excessive and medically important. All occurrences of overdose must be reported as an SAE.

## 7.7 Other Safety Considerations

Any significant worsening noted during interim or final physical examinations, scans, and any other potential safety assessments, whether or not these procedures are required by the protocol, should also be recorded as a non-serious or serious AE, as appropriate, and reported accordingly.

## 7.8 Expedited Reporting to Hospital Risk Management

Participating investigators will report to their local Risk Management office any participant safety reports or sentinel events that require reporting according to institutional policy.

CONFIDENTIAL

This document is confidential. Do not disclose or use except as authorized.

## 7.9 Monitoring of Adverse Events and Period of Observation

All adverse events, both serious and non-serious, and deaths that are encountered from initiation of study intervention, throughout the study, and within 30 days of the last study intervention should be followed to their resolution, or until the participating investigator assesses them as stable, or the participating investigator determines the event to be irreversible, or the participant is lost to follow-up. Serious adverse events will be reported from time of consent through 100 days after last dose or the start of new anti-cancer treatment, whichever comes first. The presence and resolution of AEs and SAEs (with dates) should be documented on the appropriate case report form and recorded in the participant's medical record to facilitate source data verification.

For some SAEs, the Overall PI or designee may follow-up by telephone, fax, and/or monitoring visit to obtain additional case details deemed necessary to appropriately evaluate the SAE report (e.g., hospital discharge summary, consultant report, or autopsy report).

Participants should be instructed to report any serious post-study event(s) that might reasonably be related to participation in this study. Participating investigators should notify the DF/HCC Overall Principal Investigator and their respective IRB of any unanticipated death or adverse event occurring after a participant has discontinued or terminated study participation that may reasonably be related to the study.

## 7.10 Routine Adverse Event Reporting

All Adverse Events **must** be reported in routine study data submissions to the Overall PI on the toxicity case report forms. **AEs reported through expedited processes (e.g., reported to the IRB, FDA, etc.) must also be reported in routine study data submissions.**

## 7.11 Reporting by the Study Sponsor / Overall Principal Investigator

The Sponsor will reconcile the clinical database SAE cases (case level only) transmitted to BMS Global Pharmacovigilance ([[contact]](mailto:[contact])). Frequency of reconciliation should be every 3 months and prior to the database lock or final data summary. BMS GPV&E will email, upon request from the Investigator, the GPV&E reconciliation report. Requests for reconciliation should be sent to [[contact]](mailto:[contact]). The data elements listed on the GPV&E reconciliation report will be used for case identification purposes. If the Investigator determines a case was not transmitted to BMS GPV&E, the case should be sent immediately to BMS.

As this PI-Initiated Trial does not include external sites, the Study Sponsor / Overall Principal Investigator (also the DF/HCC Overall PI) will not be circulating either of the following to participating Investigator Teams:

- Reportable AEs occurring on this study protocol.
- IND safety reports received on study.

CONFIDENTIAL

This document is confidential. Do not disclose or use except as authorized.

### **7.11.1 Expedited Reporting to the Food and Drug Administration (FDA)**

The Overall PI, as study sponsor, will be responsible for all communications with the FDA. The Overall PI will report to the FDA, regardless of the site of occurrence, any serious adverse event that meets the FDA's criteria for expedited reporting following the reporting requirements and timelines set by the FDA.

## **8. PHARMACEUTICAL INFORMATION**

A list of the adverse events and potential risks associated with the investigational agent administered in this study can be found in Section 7.1.

### **8.1 Nivolumab**

#### **8.1.1 Description**

Nivolumab (BMS-936558-01) Injection drug product is a sterile, non-pyrogenic, single-use, isotonic aqueous solution formulated at 10 mg/mL. Other names = MDX-1106, ONO-4538, and anti-PD-1. Nivolumab may be labeled as 'BMS-936558-01 Solution for Injection'.

#### **8.1.2 Form**

Nivolumab is a clear to opalescent, colorless to pale yellow liquid that may contain particles, and is provided at a concentration of 10mg/mL in 10mL vials (100 mg/vial). Vials are 10-cc Type 1 flint glass vials stoppered with butyl stoppers and sealed with aluminum seals, and cartons contain 5 or 10 vials.

#### **8.1.3 Storage, Handling, and Stability**

Please refer to the Nivolumab Pharmacy Reference Sheet for full details on storage, handling and stability information.

BMS-936558-01 Injection must be stored at 2 to 8 degrees C (36 to 46 degrees F) and protected from light and freezing

If stored in a glass front refrigerator, vials should be stored in the carton. Recommended safety measures for preparation and handling of nivolumab include laboratory coats and gloves.

For additional details on prepared drug storage and use time of nivolumab under room temperature/light and refrigeration, please refer to the BMS-936558 (nivolumab) Investigator Brochure section for "Recommended Storage and Use Conditions"

#### **Storage Conditions & Handling:**

- Store at 2-8°C (36-46°F), protect from light, freezing, and shaking.
- If any temperature excursions are encountered during storage, please report these to BMS for assessment via the Temperature Excursion Response Form.
- As with all injectable drugs, care should be taken when handling and preparing nivolumab. Whenever possible, nivolumab should be prepared in a laminar flow hood or safety cabinet using standard precautions for the safe handling of intravenous agents applying aseptic

CONFIDENTIAL

This document is confidential. Do not disclose or use except as authorized.

technique.

- Partially used vials should be disposed at the site following procedures for the disposal of anticancer drugs.

Qualified personnel, familiar with procedures that minimize undue exposure to themselves and the environment, should undertake the preparation, handling, and safe disposal of the chemotherapeutic agent in a self-contained and protective environment.

After final drug reconciliation, unused nivolumab vials should be disposed at the site following procedures for the disposal of anticancer drugs. (For sites where Institutional policy does not allow Teams to keep and store used vials for reconciliation, please ensure utilization of the NCI DAR form or equivalent.) For further information, please either discuss with your BMS CSR&O protocol manager or refer to your site IP Destruction policies and procedures.

**Use Time/Stability:** Please refer to section 3.2.3 of the current Investigator Brochure. Due to parameters surrounding the use time of Nivolumab, the time of preparation should be noted in the Pharmacy Source documents [accountability logs] or in study files as required for investigator sponsored research [FDA and GCP]

The administration of BMS-936558-01 injection prepared for dosing nivolumab infusion must be completed within 24 hours of preparation. If not used immediately, the infusion solution may be stored up to 20 hours in a refrigerator at under refrigeration conditions (2°-8°C, 36°-46°F) and used within 4 for up to 24 hours, and a maximum of 4 hours of the total 24 hours can be at room temperature (20°-25°C, 68°-77°F) and under room light. The maximum 4-hour period under room temperature and room light conditions for undiluted and diluted solutions of BMS-936558-01 injection in the IV bag should be inclusive of the includes the product administration period.

#### **8.1.4 Compatibility**

No incompatibilities between nivolumab and polyvinyl chloride (PCV) and non-PCV/non-DEHP (di(2-ethylhexyl)phthalate) containers/IV components or glass bottles have been observed. Please refer to the Nivolumab (BMS-936558-01) IB for any potential compatibility issues.

#### **8.1.5 Preparation and Administration**

##### **Dose administration**

Participants should initiate drug within 14 days of screening assessments, unless otherwise noted.

Nivolumab is to be administered on Day 1 of every cycle, as an IV infusion over 30 minutes (window of -10 / + 30 min). At the end of the infusion, flush the line with a sufficient quantity of normal saline.

Cohort 1: Nivolumab (240 mg) is to be administered every 2 weeks (on Day 1 of every 14-day cycle). There is an administration window of -2/+5 days for Nivolumab administrations; although a minimum 12-day interval (11 non-dosing days) is required between nivolumab doses.

CONFIDENTIAL

This document is confidential. Do not disclose or use except as authorized.

NOTE: Participants who have received active study therapy for  $>/=$  12 months will be allowed the option to adjust their Nivolumab dosing schedule from once every 2 weeks (-2/+5 days) to once every 4 weeks (+/- 1 week).

Cohort 2: During the initial combination phase of therapy for cohort 2, nivolumab is to be administered every 3 weeks at 3 mg/kg with ipilimumab for four doses. Thereafter, during the maintenance phase of nivolumab monotherapy, patients will receive flat dosing of 480 mg once every four weeks until discontinuation of protocol therapy (Section 5.10). There is an administration window of -2/+5 days for Nivolumab administrations

There are no premedications recommended for nivolumab on the first cycle.

There will be no dose modifications allowed.

Subjects should be carefully monitored for infusion reactions during nivolumab administration. If an acute infusion reaction is noted, subjects should be managed according to Protocol Section 5.8.3.

Doses of nivolumab may be interrupted, delayed, or discontinued depending on how well the subject tolerates the treatment.

*Nivolumab Injection, 100 mg/10 mL (10 mg/mL). Nivolumab injection is to be administered as an IV infusion through a 0.2-micron to 1.2-micron pore size, low-protein binding polyethersulfone membrane in-line filter at the protocol-specified doses. It is not to be administered as an IV push or bolus injection. Nivolumab injection can be infused undiluted (10 mg/mL) or diluted with 0.9% Sodium Chloride Injection, USP or 5% Dextrose Injection, USP to protein concentrations as low as 0.35 mg/mL. Care must be taken to assure sterility of the prepared solution as the product does not contain any antimicrobial preservative or bacteriostatic agent.*

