## TRIAL SUMMARY

Abbreviated Title	Nivolumab for Progressive/Recurrent Meningioma
Trial Phase	II
Clinical Indication	Progressive/recurrent meningioma
Trial Type	Interventional
Type of control	No treatment control
Route of administration	Intravenous
Trial Blinding	Unblinded, open-label
Treatment	
Cohort 1: Nivolumab monotherapy (240 mg every 2 weeks)
 
NOTE: Participants who have received active study therapy for >/= 6 months will be allowed the option to adjust their Nivolumab dosing schedule from 240 mg once every 2 weeks (-2/+5 days) to 480 mg once every 4 weeks (+/- 1 week).
 
Cohort 2: External Beam RT (IMRT, 3D-CRT, or proton-beam radiation therapy), followed by 4 cycles of Nivolumab (3 mg/kg every 3 weeks) + Ipilimumab (1 mg/kg every 3 weeks), followed by Nivolumab monotherapy (480 mg every 4 weeks). A safety lead-in is included for Cohort 2.

Number of trial subjects	Approximately 25 patients will be enrolled in each cohort
Estimated duration of trial	The Principal Investigator estimates that the trial will require approximately 42 months from the time the first participant of each cohort signs the informed consent until the last participant's last visit.

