## 5. TREATMENT PLAN

### 5.1 Cohort 1: Nivolumab Monotherapy Treatment Regimen

Nivolumab will be administered every 2 weeks\*, with 14 consecutive days defined as a treatment cycle.

Dosing window\*: There is an administration window of -2/+5 days for Nivolumab administrations; however, participants may be dosed no less than 12 days (11 non-dosing days) between doses.

Labs/assessments window: Labs/assessments may be performed up to 3 days prior to Nivolumab doses.

\* NOTE: Participants who have received active study therapy for  $\geq$  6 months will be allowed the option to adjust their Nivolumab dosing schedule from 240 mg once every 2 weeks (-2/+5 days) to 480 mg once every 4 weeks (+/- 1 week).

Counting of days will not be continuous on study. In the event of a treatment delay due to a toxicity, the current cycle will be extended until the criteria to resume treatment are met. The day of treatment restart will be the participant's subsequent cycle's Day 1.

If treatment with study medication is delayed  $>$  6 weeks, the participant must be permanently discontinued from study therapy, except as specified in Section 6.4.

Treatment will be administered on an outpatient basis. Reported adverse events and potential risks are described in Section 7. Appropriate dose modifications are described in Section 6. No investigational or commercial agents or therapies other than those described below may be administered with the intent to treat the participant's malignancy.

For details regarding drug storage, preparation, administration, and use time please refer to Section 8 of the protocol and the current BMS-936558 (nivolumab) Investigator Brochure.

Nivolumab is to be administered as an IV infusion over 30 minutes (window of -10 / + 30 min). At the end of the infusion, flush the line with a sufficient quantity of normal saline.

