#### **Selection and Timing of Dose for Each Participant**

The dosing regimen and schedule of nivolumab are detailed in Table 5.1-1.

Table 5.1-1 Dosing Schedule for Cohort 1					
Cycles = 2 weeks (Nivolumab dosing every 2 weeks) *					
	Cycle 1 Day 1	Cycle 2 Day 1	Cycle 3 Day 1	Cycle 4 Day 1	Cycle 5 Day 1
Nivolumab Dose	240 mg				

\* NOTE: Participants who have received active study therapy for  $\geq$  6 months will be allowed the option to adjust their Nivolumab dosing schedule from 240 mg once every 2 weeks (-2/+5 days) to 480 mg once every 4 weeks (+/- 1 week).

CONFIDENTIAL

This document is confidential. Do not disclose or use except as authorized.

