### Dosing Modifications/Reductions:

Dose reduction outside of the safety lead-in is not permitted on study for any reason; there will be no dose reductions allowed for the management of toxicities of individual participants. Dose

CONFIDENTIAL

This document is confidential. Do not disclose or use except as authorized.

delays for the management of study treatment related adverse events are described in this section. Of note, given the overlapping toxicities associated with nivolumab and ipilimumab, dose delay criteria specified below should be applied to participants in Cohort 2 who develop a potential immune related adverse event while receiving combined nivolumab plus ipilimumab therapy. In addition, participants who require discontinuation of ipilimumab due to immune related adverse events as defined below, may be allowed to resume study nivolumab therapy if the treating clinician feels that the adverse event was more likely related to ipilimumab therapy than nivolumab therapy. Participants who discontinue ipilimumab and resume nivolumab therapy will follow the monotherapy nivolumab dosing schedule of 480 mg every 4 weeks.

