### **6.2 Dose Modifications**

Dose reductions or dose escalations are not permitted.

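### Section 8.1.5 opens the Cohort 1 switch to 4-weekly nivolumab at 12 months with no dose stated; six other places open it at 6 months at 480 mg

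*Combined protocol and SAP*

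**What the plan says.** Section 8.1.5 (Preparation and Administration) sets Cohort 1 nivolumab at 240 mg on Day 1 of each 14-day cycle. A note then says that participants on active study therapy for at least "12 months will be allowed the option to adjust their Nivolumab dosing schedule from once every 2 weeks" to once every 4 weeks. The note changes the interval only and gives no milligram dose. The 480 mg that appears later in the section is the Cohort 2 maintenance dose. The same section adds: "There will be no dose modifications allowed".

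Section 5.1 says otherwise. Under its subheading on selection and timing of dose it states that "The dosing regimen and schedule of nivolumab are detailed in Table 5.1-1". The note to that table says that participants treated for at least "6 months will be allowed the option to adjust their Nivolumab dosing schedule from 240 mg once every 2 weeks (-2/+5 days) to 480 mg" every 4 weeks. The same 6-month, 480 mg rule stands in the Trial Summary, the Section 5.1 text, Section 5.7, Section 5.8.1.1 and Study Calendar footnote aa.

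Section 5.1 also directs the reader onward: "For details regarding drug storage, preparation, administration, and use time please refer to Section 8 of the protocol". The closing text of Section 5.8.1.1 likewise sends the reader to Section 8 for handling, dispensing and infusion information.

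**The concern.** All seven statements are current, operative text, and they give different answers on two points: when the option opens and what dose goes with it. A participant at month 8 may switch under Section 5.1 and may not under Section 8.1.5. A pharmacist working from 8.1.5 finds 240 mg as the only Cohort 1 dose and nothing for the 4-weekly interval. The two sections devoted to administration, 5.8.1.1 and 8.1.5, disagree with each other, and the one with the fuller rule points on to the one without it.

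A related ambiguity concerns the ban on dose changes. Section 6.2 says "Dose reductions or dose escalations are not permitted", and 8.1.5 bars dose modifications, yet the switch takes a single infusion from 240 mg to 480 mg. Neither section says that the switch is exempt.

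At stake are consistent dosing in Cohort 1 and the number of infusion visits. The trial's inference is not at stake.

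**Working it through.** **Step 1: set the statements side by side.**

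| Place | Switch opens at | Dose before | Dose after |
|---|---|---|---|
| Trial Summary, Treatment row | 6 months | 240 mg every 2 weeks | 480 mg every 4 weeks |
| Section 5.1, text | 6 months | 240 mg every 2 weeks | 480 mg every 4 weeks |
| Section 5.1, note to Table 5.1-1 | 6 months | 240 mg every 2 weeks | 480 mg every 4 weeks |
| Section 5.7 | 6 months | 240 mg every 2 weeks | 480 mg every 4 weeks |
| Section 5.8.1.1 | 6 months | 240 mg every 2 weeks | 480 mg every 4 weeks |
| Section 10, footnote aa | 6 months | 240 mg every 2 weeks | 480 mg every 4 weeks |
| **Section 8.1.5** | **12 months** | not in the note (240 mg every 2 weeks earlier in the section) | **none stated, every 4 weeks** |

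Six places agree and one differs. Table 5.1-1 is named as the place where the schedule is detailed, so 8.1.5 is the text to correct.

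**Step 2: effect of the timing conflict.** The interval in dispute is months 6 to 12, taken as 26 weeks.

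- Stay on 240 mg every 2 weeks: 26 / 2 = 13 infusions; 13 × 240 = 3,120 mg; 3,120 / 26 = 120 mg/week.
- Switch to 480 mg every 4 weeks: 26 / 4 = 6.5 infusions on average (6 or 7 in practice); 6.5 × 480 = 3,120 mg; 3,120 / 26 = 120 mg/week.

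The conflict changes the number of infusions by 13 − 6.5 = 6.5 per participant, that is, 6 or 7. It leaves average dose intensity unchanged.

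**Step 3: effect of the missing dose, on a literal reading only.** Suppose a reader of 8.1.5 lengthens the interval and keeps 240 mg. Then 6.5 × 240 = 1,560 mg over 26 weeks, and 1,560 / 26 = 60 mg/week, half the intended intensity. This is an assumption about how a reader might fill the gap. No section prescribes 240 mg every 4 weeks.

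**Step 4: how many participants could be affected.** Section 14.1.4 plans 25 patients per cohort, with PFS-6 of 26% under the null and 51% under the alternative. Assume that those progression-free at 6 months are those still on therapy:

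- 25 × 0.26 = 6.5, about 7.
- 25 × 0.51 = 12.75, about 13.

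**Step 5: effect on the primary analysis.** The switch opens at 6 months at the earliest, when PFS-6 is already determined by time on study. The threshold of 10 progression-free patients out of 25, the alpha and the power do not depend on it.

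**The case against.** The strongest reply is that the protocol read as a whole settles the matter. Six places agree and Table 5.1-1 is named as the schedule. The pointer to Section 8 covers storage, preparation, administration and use time rather than schedule, and it sits in a section that itself carries the 6-month rule. Section 8.1.5 also says elsewhere that infusions are given at the doses the protocol specifies, so it can be read as deferring to the 480 mg set out in the other sections. This shows that a careful reader would reach the right answer, which is why the point is minor. It does not make the 12-month note correct.

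Second, the timing error is in the safe direction. The switch is optional. Someone held to 12 months stays on a compliant regimen, and a switch at 12 months or later also meets the 6-month rule. Scans follow calendar days, so imaging is not disturbed. All of this stands.

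Third, the ban on dose changes is explained in Section 6 by reference to toxicity: "there will be no dose reductions allowed for the management of toxicities of individual participants". The switch also keeps the weekly dose equal, so it is unlikely that the ban was meant to catch it. A clarifying clause is useful but not essential.

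Fourth, the reach figure is rough. It ignores stopping for toxicity and treatment continued past initial radiologic progression. Section 2.4 reports one near-complete response and stable disease in 20–25% of Cohort 1. That is not a PFS-6 figure, but it lends no support to the upper end of the range. Section 1 opens Cohort 2 only after Cohort 1 enrolment is complete, so few future switches may remain. Treatment may continue indefinitely under Section 5.10, however, so the number need not be zero.

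**Conclusion.** The inconsistency is real and Section 8.1.5 is wrong as written, on both the threshold (12 months against 6) and the omitted 4-weekly dose. Severity is minor. The certain consequence is a permitted switch delayed by up to 6 months for anyone dosed from 8.1.5 alone, costing 6 or 7 extra infusions per participant at an unchanged 120 mg/week. The halving to 60 mg/week is conditional on a literal misreading and should not be taken as a protocol instruction. The range of about 7 to 13 participants rests on equating progression-free status at 6 months with still being on therapy, and actual numbers may be lower. The documents do not show that any switch was made under the 8.1.5 wording. There is no effect on PFS-6, the decision rule, alpha or power.

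**What to change.** Replace the note in Section 8.1.5 with the Section 5.1 rule: at least 6 months on active therapy, 240 mg every 2 weeks to 480 mg every 4 weeks, with the same windows. In 8.1.5 and 6.2, add a clause saying that this optional switch is not one of the barred dose changes. Check the Cohort 1 dosing records for the date and dose of any switch already made. The dose matters more, since a switch at 12 months or later already satisfies the 6-month rule.

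The cost is a short wording change and a limited records check. Design and analysis are unchanged.
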